11.8. Modified Clinical Global Impression – Rater Version (MCGI-R)

The MCGI-R includes 2 items:

- A 7-point scale that allows clinicians to rate the severity of a subject's opiate withdrawal symptoms.
- A 4-point scale that allows clinicians to rate the degree of a subject's side effects from study drug.

A copy of the MCGI-R is provided in Section 16.10.

11.9. EuroQol 5-Dimension 5-Level (EQ-5D-5L)

The EQ-5D-5L is a health state utility instrument that evaluates preference for health status (utility). The 5 items in the EQ-5D-5L comprise 5 dimensions (mobility, self-care, usual activities, pain/discomfort, and anxiety/depression) each of which are rated on 5 levels of severity. Responses to the 5 items encode a discrete health state which is mapped to a preference (utility) specific for different societies. Subjects also rate their perception of their overall health on a separate visual analogue scale.

A copy of the EQ-5D-5L is provided in Section 16.11.

11.10. Short Form Health Survey – 36 Items (SF-36)

The SF-36 assesses 8 health concepts: physical functioning, bodily pain, role limitations due to physical health problems, role limitations due to personal or emotional problems, emotional well-being, social functioning, energy/fatigue, and general health perceptions. It also includes a single item that provides an indication of perceived change in health.

A copy of the SF-36 is provided in Section 16.12.

11.11. Subject Satisfaction Questionnaire

Subject satisfaction will be scored from 0 (very satisfied) to 4 (very dissatisfied) based on the following question: Overall, how would you rate your satisfaction with the treatment you received in this study to help you discontinue using your opioid?

- 0 = very satisfied
- 1 = satisfied
- 2 = neither satisfied nor dissatisfied
- 3 = dissatisfied
- 4 = very dissatisfied

A copy of the Subject Satisfaction questionnaire is provided in Section 16.13.

11.12. Subject Interview

The primary purpose of the qualitative interview is to provide additional data to augment the data collected from quantitative instruments to assess withdrawal, pain intensity, quality of life, treatment satisfaction, and others. The results of this interview will provide information that may be useful for planning future studies to evaluate the safety and efficacy of LUCEMYRA in the setting of an opioid taper in subjects with chronic non-cancer pain. The interview will be conducted via a centralized interviewer through a phone call. The interview should take place no more than 5 days after the EOS Visit.

The qualitative interview will be designed to collect information about: (1) subjects' experiences with opioid withdrawal syndrome while gradually tapering their opioids and the relevance, utility, and interpretability of the opioid withdrawal scales used in the study to assess their opioid withdrawal symptoms; (2) factors that may facilitate or interfere with subject recruitment and retention in a large clinical trial for the discontinuation of opioid therapy; (3) subjects' experiences in the clinical trial, including questions about how they would improve the experience and whether they would participate in future trials; and (4) subjects' experiences and preferences regarding the treatments administered in the clinical trial. Questions will be organized from more general (open-ended) to more specific.

Audio from each interview will be recorded.

12. ASSESSMENTS OF SAFETY

Safety assessments will be performed at the time points outlined in Table 2, Table 3 and Table 4.

12.1. Safety Parameters

12.1.1. Demographic/Medical History

The medical history will include demographic information, current co-morbidities, relevant past illnesses, and surgical procedures performed within the prior 6 months. Assessments will also include characterization of the subject's baseline pain state, condition, opioid use, and opioid withdrawal history.

12.1.2. Vital Signs

Orthostatic vital signs will be measured in-clinic. Orthostatic vital signs will be measured first after the subject has been sitting for at least 5 minutes (systolic/diastolic blood pressure, pulse, and temperature) and then after the subject has been standing for at least 3 minutes (systolic/diastolic blood pressure and pulse). On Day 1, orthostatic vital signs should be assessed pre-dose and 1-hour post-dose of study drug. A post-dose assessment is not required after Day 1. When repeat vital signs are performed, temperature does not need to be collected (only systolic/diastolic blood pressure and pulse).

Resting vital signs (systolic/diastolic blood pressure and pulse) only will be measured at home using a vital sign monitor during phone calls after dose reductions, and every day during the 4-day study drug taper through the EOS Visit. Resting vital signs will be measured after the subject has been sitting quietly for at least 5 minutes and, during the study drug taper and after, will be taken twice daily, once in the morning and once in the evening.

Subjects should contact the Investigator if they experience signs or symptoms of hypotension, bradycardia, or orthostasis (eg, lightheadedness, slow heart rate, dizziness, feeling faint at rest or when standing up) or hypertension (eg, pounding headache, dizziness, palpitations). Subjects should contact the Investigator if they record an at-home vital signs measurement reaching or exceeding a systolic blood pressure of ≥ 180 mmHg, diastolic blood pressure ≥ 105 mmHg, or heart rate of ≥ 120 bpm. Symptomatic episodes of hypotension should be captured as an AE. Confirmed instances of meeting criteria for hypertension should be captured as AEs regardless of symptomology.

During phone calls, the Investigator should ask the subject for a vital sign measurement and review subject-measured at-home vital signs.

Blood pressure and pulse measurements taken in-clinic or at-home should be repeated after a 15-30 minute rest if they meet the following criteria:

- Hypertension: systolic blood pressure of ≥180 mmHg, diastolic blood pressure ≥105 mmHg, or heart rate of ≥120 bpm
- Hypotension: systolic blood pressure of ≤90 or a diastolic blood pressure of ≤60, and a heart rate <50 bpm

If the subject has a confirmed systolic blood pressure of ≥ 180 mmHg, diastolic blood pressure ≥ 105 mmHg, or heart rate of ≥ 120 bpm, and is symptomatic, the subject should be seen (preferably by the Investigator).

If the subject has a confirmed systolic blood pressure of ≤ 90 or a diastolic blood pressure of ≤ 60 , and a heart rate < 50 bpm, and is symptomatic, the Investigator should advise the subject to either decrease or hold the next dose of study drug.

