Enhanced treatment options for emerging opioid withdrawal symptoms during opioid taper regimens may permit development of more efficient tapering protocols, which in turn would have significant

impact on reducing risk to patients on chronic opioids and may positively impact health economic outcomes.

There is a notable lack of well-controlled data on the opioid withdrawal syndrome during an opioid taper in chronic non-cancer pain patients. Gradually tapering a patient's opioid dose with small reductions in dose over a prolonged period of time is a practice inherently designed to mitigate the potential for opioid withdrawal. LUCEMYRA's effectiveness in treating opioid withdrawal symptoms has been established in the setting of abrupt opioid discontinuation; however, has not been thoroughly evaluated in the setting of an opioid taper. Opioid tapers are often conducted over several weeks, if not months, resulting in the potential for at least cumulative use of LUCEMYRA for beyond 14 days. A clinical trial is necessary to assess for a signal of serious hypotension, bradycardia, syncope, hepatotoxicity, or rebound hypertension, or identify potential unexpected serious risks of long-term use of LUCEMYRA in the setting of an opioid taper as the majority of the existing safety data for LUCEMYRA is on less than 14 days of use. This pilot study is intended to inform critical study design elements for a future pivotal study to assess the safety and efficacy of LUCEMYRA for use beyond 14 days in the setting of an opioid taper.

Methodology:

This is a pilot, multicenter, randomized, double-blind, placebo-controlled, outpatient clinical trial to assess the safety and tolerability, and to estimate the effectiveness of LUCEMYRA for mitigating the symptoms of opioid withdrawal in the setting of an opioid taper in subjects with chronic non-cancer pain.

After a Screening period of up to 28 days, subjects will begin a planned 14-day complete taper of their pre-study opioid and will be randomly assigned (1:1) to either LUCEMYRA or matching placebo. Study drug will be administered through the opioid taper and for 5 days after the opioid taper is completed. Study drug will then be tapered over a 4-day period for a total of approximately 21 days exposure to study drug (Figure 1).

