6. TRIAL OBJECTIVES AND PURPOSE

6.1. **Primary Objective**

The primary objective is to evaluate the safety and tolerability of LUCEMYRA versus placebo when used during an opioid taper in subjects with chronic non-cancer pain.

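### AE recording is symptom-gated for hypotension but not for hypertension, so the two TEAE rates are not comparable and asymptomatic hypotension is under-counted

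*Combined protocol and SAP*

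**What the plan says.** All of the recording rules are in protocol Section 12.1.2 (Vital Signs).

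- AE rule, low pressure: "Symptomatic episodes of hypotension should be captured as an AE".
- AE rule, high pressure: "Confirmed instances of meeting criteria for hypertension should be captured as AEs regardless of symptomology".
- Criterion for repeating a low reading: "Hypotension: systolic blood pressure of ≤90 or a diastolic blood pressure of ≤60, and a heart rate <50 bpm".
- Criterion for repeating a high reading: "Hypertension: systolic blood pressure of ≥180 mmHg, diastolic blood pressure ≥105 mmHg, or heart rate of ≥120 bpm".
- Subjects are to call the site "if they record an at-home vital signs measurement reaching or exceeding a systolic blood pressure of" 180 mmHg, or the matching diastolic and heart rate limits. For low pressure or slow heart rate they are to call on signs or symptoms; no reading triggers a call.
- In-clinic timing: "A post-dose assessment is not required after Day 1".

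On purpose, Section 6.1 states: "The primary objective is to evaluate the safety and tolerability of LUCEMYRA versus placebo when used during an opioid taper". The Rationale in the Synopsis adds: "A clinical trial is necessary to assess for a signal of serious hypotension, bradycardia, syncope, hepatotoxicity, or rebound hypertension".

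Section 7.2.1 lists seven safety endpoints without ranking them. TEAE incidence is the first, and change in vital signs from Baseline is another. Section 13.4.2 makes all safety summaries descriptive. Section 13.4.2.1.4 leaves the criteria for potentially clinically significant vital signs to the SAP.

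**The concern.** The two AE rules stand in adjacent sentences. One depends on the subject feeling something; the other expressly does not. No reason for the difference is given. A reader of the TEAE table would naturally set the hypotension row beside the hypertension row, but the two rows count different things: symptomatic episodes in one, confirmed readings in the other.

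With no safety testing planned, descriptive counts carry the safety conclusion, so the way events are ascertained matters. The trial is also meant to inform a pivotal study. A hypotension rate taken from the TEAE table would pass a symptomatic-only figure into that planning.

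**Working it through.** **Side-by-side reading of Section 12.1.2**

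| | Low | High |
|---|---|---|
| AE instruction | symptomatic episodes | confirmed readings, symptoms irrelevant |
| Repeat criterion | (SBP ≤90 or DBP ≤60) and HR <50 | SBP ≥180, or DBP ≥105, or HR ≥120 |
| Call-in on a reading | none stated | yes, same limits |

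In the standard schedule (Tables 2 and 4), vital signs on Days 1 to 17 are taken on seven days: 1, 2, 3, 7, 8, 14 and 15. Twice-daily home readings begin on Day 18, when the study drug taper starts, and run to the EOS Visit. Readings are therefore sparse during full dosing and dense in the period when rebound could appear.

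**The plan's own precision figure**

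No stated figure bears directly on this point. The only design calculation is in Section 13.2: a half-width of 0.24 at 20 per group and 0.17 at 40 per group for a difference of 0.2. The arm rates are not given in the text. Taking 0.1 and 0.3, the uncorrected Wald half-width is

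1.96 × √[(0.1×0.9 + 0.3×0.7)/n] = 1.96 × √(0.30/n)

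This gives 0.240 at n = 20 and 0.170 at n = 40, matching the plan, and 0.196 at the planned n = 30.

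**Effect of the symptom gate on the recorded difference**

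Let pL and pP be the true proportions with hypotension on lofexidine and placebo, and s the share of those subjects who are symptomatic, equal in both arms. Then

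recorded difference = s × (pL − pP)

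Assume pL = 0.30 and pP = 0.10 with 30 per arm. All three inputs other than the sample size are assumptions. The Wald intervals are for scale only.

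| s | Recorded rates | Difference (95% CI) | Expected cases |
|---|---|---|---|
| 1.00 | 0.300 vs 0.100 | 0.20 (0.004 to 0.396) | 9 vs 3 |
| 0.75 | 0.225 vs 0.075 | 0.15 (−0.03 to 0.33) | 6.75 vs 2.25 |
| 0.50 | 0.150 vs 0.050 | 0.10 (−0.05 to 0.25) | 4.5 vs 1.5 |
| 0.25 | 0.075 vs 0.025 | 0.05 (−0.06 to 0.16) | 2.25 vs 0.75 |

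At 50% versus 10% the true difference of 0.40 becomes 0.30, 0.20 and 0.10 for the same three shares below 1.

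The under-count within each arm follows for any s < 1. The shrinkage of the difference also needs the equal-share assumption. With s = 0.75 on lofexidine and 0.25 on placebo, 0.30×0.75 − 0.10×0.25 = 0.20, and the difference does not shrink.

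**Why no net direction follows**

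Hypertension passes through no symptom gate, so its difference is recorded in full. If high readings come mainly from withdrawal, say 5% on lofexidine and 15% on placebo, the recorded difference is −0.10. If they come mainly from rebound, say 15% and 5%, it is +0.10. Set beside a recorded hypotension difference of 0.10 (s = 0.50), full capture of hypertension works for the active arm in the first case and against it in the second.

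**The case against.** A reader might infer that the rule makes the active arm look safer overall, by counting withdrawal harm in full and drug harm in part. The documents do not support that. The Rationale names rebound hypertension among the signals to be assessed, and home readings are densest in the rebound window. Nor is there a single primary AE comparison to bias: safety is the primary objective, and several unranked descriptive endpoints serve it.

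A reader might also infer that the joint low criterion decides which hypotension becomes an AE. It does not. It governs repeat readings and, for symptomatic subjects, advice on the next dose. The hypotension AE sentence carries no numeric limit and needs no confirmation, so for symptomatic episodes it is looser than the hypertension rule.

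Other points on that side stand in part:

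- Section 12.1.2 does not forbid recording asymptomatic hypotension, and the AE definition in Section 12.2.1.1 is broad enough to include it. But the specific instruction is what sites will follow, and discretion across 7 centers would make capture uneven.
- Measured vital signs are analysed whatever the AE coding. So this is a gap in the TEAE tables, not a loss of all hypotension data. But a summary of change from Baseline by visit does not show how many subjects reached a low value.
- The SAP may define threshold criteria. It is still to be finalised under Section 13.1, so such a table cannot be called missing. It would not alter the AE rule in any case.
- The Rationale speaks of serious hypotension, and a reading without symptoms need not be serious. That limits the importance of the point without making the two AE rows comparable.

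**Conclusion.** The concern holds in a limited form. AE capture depends on symptoms for hypotension and not for confirmed hypertension, and reading-based call-in exists only on the high side. Hypotension and hypertension TEAE rates are therefore not comparable, and asymptomatic hypotension is under-counted in the TEAE tables where sites follow the instruction.

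The size cannot be determined from the documents. The halving of a 20-point difference is an illustration that rests on assumed rates of 30% and 10% and a symptomatic share of one half in both arms. With equal shares the risk ratio is unchanged (3 to 1), and the 10-point change lies inside the half-width of about 20 points at 30 per arm. The net direction over all AEs is also undetermined. The point concerns ascertainment and calls for a correction; it does not show that the plan favours the drug.

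**What to change.** 1. In Section 12.1.2, keep AE capture of every symptomatic hypotension episode and add AE capture of confirmed low readings regardless of symptoms, on the same basis as high readings. The addition must not replace the symptomatic rule, or episodes now recorded without a confirmed reading would be lost.
2. In the SAP, before database lock, specify a table by arm of the number of subjects with any SBP ≤90, any DBP ≤60 and any HR <50, each separately, beside any SBP ≥180, any DBP ≥105 and any HR ≥120. Use all measured vital signs, regardless of symptoms or AE coding. These are the protocol's own cut-offs and the data are already collected.
3. Ask the sponsor to confirm whether the low criterion in Section 12.1.2 is meant to require low pressure and HR <50 together, and to reconcile the wording. As written, HR <50 alone, or low pressure with a higher heart rate, meets no repeat criterion, while the high limbs each stand alone. The confirmed low readings in item 1 depend on the answer; the table in item 2 does not. No clinical threshold or management rule is proposed here.

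The cost is amendment wording, some extra AE lines and one table. Hypotension counts will look less favourable than under the present rule.

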8.2. Subject Exclusion Criteria

- 1. Has a primary diagnosis of complex regional pain syndrome, central neuropathic pain, somatoform pain syndromes, acute nerve root compression, any acute or progressive infectious, inflammatory, or neurological process.
- 2. Liver disease that requires medication or medical treatment, and/or AST or ALT levels greater than 3 times the ULN.
- 3. Gastrointestinal or renal disease, which would significantly impair absorption, metabolism or excretion of study drug, or would require medication or medical treatment.
- 4. Has a diagnosis of epilepsy or history of seizures.
- 5. Has clinically significant abnormal laboratory value(s).
- 6. Self-reported or evidence of OUD or other substance use disorder within last 12 months prior to Screening using the Sponsor-provided Mini-International Neuropsychiatric Interview.
- 7. Urine toxicology screen positive for any illicit or non-prescribed opioid drugs prior to randomization.
- 8. Taking prescription methadone, buprenorphine, fentanyl rapid acting products, tapentadol, tramadol, butorphanol, meperidine, or levorphanol for any reason.

- 9. Known or suspected pregnancy, planned pregnancy, or lactation.
- 10. Any of the following cardiovascular abnormalities at Screening and before randomization:
 - a. Resting heart rate ≥ 105 bpm or <55 bpm or symptomatic bradycardia;
 - b. Resting systolic blood pressure ≥160 mmHg or <95 mmHg or symptomatic hypotension;
 - c. Resting diastolic blood pressure \geq 90 mmHg or <65 mmHg;
 - d. Clinically significant abnormal electrocardiogram (eg, second- or third-degree heart block, uncontrolled arrhythmia; QT corrected by heart rate by Fridericia's method (QTcF) of ≥450 msec or a history of QT interval prolongation;
 - e. New York Heart Association class III or IV; or
 - f. History of myocardial infarction within 6 months of Screening.

Medications taken for stable hypertension are permitted when dose/regimen has been consistent for a minimum of 3 months prior to screening.

- 11. Any severe or unstable psychiatric disorder including post-traumatic stress disorder, schizophrenia, bipolar disorder, major depression, substance abuse, or suicidality as determined by the Investigator.
- 12. Subject answers "yes" to "suicidal ideation" in prior 24 months to any items 1 through 5 on the C-SSRS, or subject answers "yes" to any lifetime "suicidal behavior" item on the C-SSRS.

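### Section 12.1.2 acts on a low reading only when low blood pressure and a pulse below 50 occur together, and its home contact limits have no low values

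*Combined protocol and SAP*

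**What the plan says.** Section 12.1.2 sets two criteria for repeating a clinic or home reading after a 15-30 minute rest. The high one is "Hypertension: systolic blood pressure of ≥180 mmHg, diastolic blood pressure ≥105 mmHg, or heart rate of ≥120 bpm". The low one is "Hypotension: systolic blood pressure of ≤90 or a diastolic blood pressure of ≤60, and a heart rate <50 bpm". The closing sentence of the section takes the low combination again, once confirmed: "and is symptomatic, the Investigator should advise the subject to either decrease or hold the next dose of study drug".

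For readings at home, subjects are to contact the Investigator "if they record an at-home vital signs measurement reaching or exceeding a systolic blood pressure of" 180 mmHg, or at a diastolic pressure of 105 mmHg or a heart rate of 120 bpm. No lower limits are given. On the low side, contact depends on signs or symptoms, and the examples include a slow heart rate. Adverse event capture is also symptom-led: "Symptomatic episodes of hypotension should be captured as an AE".

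Entry is handled differently. Section 8.2, criterion 10, excludes on "Resting heart rate ≥ 105 bpm or <55 bpm or symptomatic bradycardia" and, separately, on "Resting systolic blood pressure ≥160 mmHg or <95 mmHg or symptomatic hypotension". Criterion 10c does the same for diastolic pressure below 65 mmHg.

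**The concern.** There are two separate gaps.

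1. The low criterion joins pressure and pulse with *and*. Low pressure with a normal pulse, or a slow pulse with normal pressure, meets neither the repeat rule nor the dose-advice rule. The synopsis rationale lists serious hypotension and bradycardia as distinct signals, and section 8.2 screens for each low value separately. The on-study numeric rule is therefore narrower than the hazards the protocol names. It covers clinic and phone readings as well as the diary, including the reading one hour after the first dose and the Day 2 phone reading, when the dose is planned to double.

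2. Whatever the conjunction, no low number recorded at home prompts a call. In the diary period an isolated low reading without symptoms waits for the next planned contact.

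What is at stake is subject protection. The analysis is not affected.

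**Working it through.** The plan gives no figure to reproduce. The check is logical, followed by a count from the schedules.

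**Step 1: the rules applied to example readings.** Reading A is the natural one, because of the comma before the heart-rate clause: (SBP ≤90 or DBP ≤60) and HR <50. Reading B is the other possible parse: SBP ≤90 or (DBP ≤60 and HR <50). The third rule joins all three limits with *or*.

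| SBP/DBP, HR | A | B | All *or* | Home contact limit met |
|---|---|---|---|---|
| 85/55, 70 | no | yes | yes | no |
| 70/40, 52 | no | yes | yes | no |
| 85/70, 70 | no | yes | yes | no |
| 110/55, 70 | no | no | yes | no |
| 120/75, 42 | no | no | yes | no |
| 85/55, 48 | yes | yes | yes | no |
| 110/58, 48 | yes | yes | yes | no |
| 185/80, 80 | no | no | no | yes |
| 120/80, 125 | no | no | no | yes |

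Low values that trigger a repeat on their own: 0 of 3 under A, 1 of 3 (SBP) under B, 3 of 3 with *or*. High values: 3 of 3. Low values that exclude on their own at entry (HR <55, SBP <95, DBP <65): 3 of 3.

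**Step 2: home readings per subject** (Tables 2 to 5).

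- Standard schedule: phone readings on Days 2, 7 and 14 = 3. Diary, Days 18-27, twice daily = 10 × 2 = 20. Total 23. The drug taper covers Days 18-21, so on-drug readings are 3 + 4 × 2 = 11, of which 8 are in the diary.
- Pause schedule: phone readings on Days 2, 7, 14 and 20 = 4. Diary, Days 24-33 = 20. Total 24. On drug: 4 + 8 = 12.

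**Step 3: wait until a planned contact.** Standard contacts in the diary period fall on Days 19, 22, 25 and 28. Counting from each of Days 18 to 27 to the next later contact gives 1, 3, 2, 1, 3, 2, 1, 3, 2, 1 days, so the maximum is 3. Pause contacts on Days 25, 28, 31 and 34 give the same sequence.

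**Step 4: on-drug diary readings first reviewed after the last dose.** Days 20 and 21 give 2 × 2 = 4, first seen at the Day 22 visit. Day 19 adds 0, 1 or 2, depending on when that day's call is made. The result is 4 to 6 of 8, or 5 if the call falls between the two readings. The pause schedule gives the same range.

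Steps 3 and 4 use nominal days, without the ±1 day visit window. They also assume that the Day 19 and Day 25 calls review vital signs, as footnote j of Table 2 says, although the vital-signs row of that table is not marked for those calls. If the Day 19 call did not review them, all 4 × 2 = 8 on-drug diary readings would wait for Day 22.

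**The case against.** The strongest case against accepts the reading of the text and disputes its weight.

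- **Other on-study rules treat the hazards separately.** Section 8.5 allows discontinuation for persistent signs or symptoms of hypotension or of bradycardia, for a single episode of symptomatic bradycardia with specified features whatever the blood pressure, and for other significant cardiovascular findings. Section 9.5 has subjects with symptoms call before the next dose, and staff then decide on delay, omission or a visit. Sections 9.2.3 and 9.3 leave dosing open to change after each post-reduction call. This stands for subjects with symptoms, and it leaves the decrease-or-hold half of the first gap with little practical content.
- **A pulse of 42 on the monitor could count as a sign.** That is arguable, but the instruction gives no number and a subject without symptoms may not recognise it.
- **Clinic and phone readings reach staff at once.** Section 12.1.2 states that "Orthostatic vital signs will be measured in-clinic", and visits also include an ECG, auscultation and the COWS resting pulse. Each scheduled phone reading nominally precedes a visit by one day. This narrows the gap mainly to the diary. Staff may repeat a low reading on their own judgement, but the rule does not ask them to.
- **High-only home limits may be deliberate.** The diary begins with the drug taper, rebound hypertension is a named signal, and 12 of the 20 diary readings (Days 22-27, 6 × 2) fall after the last dose. This is plausible and cannot be settled from the documents. It does not explain why a repeat measurement should need a pulse below 50.
- **The fix specifies no dosing action for the subject without symptoms.** True. It brings a repeat and a call, and the decision stays with the Investigator.

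None of these routes supplies a low numeric trigger, so the gap remains, though small.

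**Conclusion.** The concern holds. Under the natural reading of section 12.1.2, no single low value prompts a repeat or supports the dose advice. Under the alternative parse only systolic pressure does. The home contact limits have no low side under either reading.

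The practical remainder is mainly the isolated low reading without symptoms, chiefly in the diary: 8 on-drug diary readings per subject, 4 to 6 of them first reviewed after the last dose, with a wait of at most 3 nominal days on the assumptions above. These are counts of opportunities and do not measure risk. The documents do not allow an estimate of how many subjects would have such a reading.

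The risk is limited because drug is being reduced or has stopped in the diary period, subjects with symptoms have other cover, and section 13.4.2.1.4 still summarizes scheduled vital signs. The change is worth making because it protects subjects cheaply. It is not a reason to hold the trial.

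**What to change.** - In the repeat criterion of section 12.1.2, ask for a second reading when SBP is ≤90, *or* DBP is ≤60, *or* HR is <50. The medical team may prefer a lower diastolic cut-off, since entry allows 65.
- In the closing sentence of 12.1.2, advise lowering or withholding the next dose when any one of these is confirmed and the subject has symptoms.
- Add the same low limits to the home contact rule in 12.1.2. Footnote r of Tables 2 and 3 already points to the contact criteria, so the change carries into subject training. Naming the low limits there as well would remove doubt.

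The cost is a wording change, site notification, and some extra repeats and calls on monitors that subjects already have. The extra load depends on how close subjects start to the limits. From the lowest values allowed at entry, a fall of 5 mmHg in systolic (95 to 90) or diastolic pressure (65 to 60), or of 6 bpm in pulse (55 to 49), would trigger a repeat. That is the reason to leave the diastolic cut-off open.
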